Evaluation of the efficacy of allogeneic umbilical cord derived hematopoietic stem cells and mesenchymal stromal cells in patients with spastic cerebral palsy on developmental function , A Clinical trial phase II

Protocol ID : IRCT201706176907N13

Document Date: January 18, 2017

Brief Summary:

Background information: Cerebral palsy (CP) consisted of a group of developmental disability in the field of motor milestones. At the present time there is no standard curative medical or surgical treatment for it .Stem cell therapy is one of a new and hopeful therapeutic methods of therapy for CP.

Objectives :This study designed for the evaluation of safety and therapeutic effects of intrathecal hematopoietic (MNC) and mesenchymal stem cells (MHC) derived from allogeneic umbilical cord in change and probable improvement of developmental functions of spastic CP participants in comparison with control group .

Study design: 108 cases of Spastic CP patients between 4-14 years old that referred to Children's Medical Center affiliated to Tehran University of Medical Sciences and had our inclusion criteria selected and randomly divided in 3 groups of MNC, MHC and control participants. One intrathecal injection of stem cell was done for intervention groups and simulation of intrathecal injection without awareness of participants prepared for control group. All of the participants had a baseline brain neuroimaging and underwent a complete exams with our outcome measure scales and neurorehabilitation with similar protocol performed for both intervention and control groups. Follow up evaluations until 12 months and brain neuroimaging at the end of 12 months will be done for participants. This study is double blind and participants and evaluators are not aware of the groups.

Detailed description:

Background information:

Cerebral palsy (CP) is characterized by aberrant control of movement or posture of a patient, appearing early in life, and not the result of a recognized progressive or degenerative brain disease. CP is an umbrella term and represents a group of conditions (not a single disorder), has a broad range of expression with a static condition originally within the developing central nervous system.

CP is a disturbance of movement and or posture. CP is a static neurologic condition resulting from brain injury that occurs during the first two years of life.

CP can result from brain injury occurring during the prenatal, perinatal, or postnatal periods. Seventy to 80 percent of patients with CP have spastic clinical features. In developed countries CP occurs in approximately 2.5/1000 live births.

At present, conventional therapies for children with CP include medications, orthopedic and neurosurgical intervention and neurorehabilitation, but none of these treatments can fundamentally repair damaged neural cells. Stem cells have been investigated as a treatment for neurological damage since the 1990s. There are a number of developmental disorders that are considered targets for stem cell therapy. The most well-known and studied is CP. Stem cell therapy is a new and promising treatment of neurological disorders including CP. For using neurological trial, neurons and glial cells have been generated from Pluripotential stem cells and Multipotential somatic stem cells. There is little clinical trial for stem cell therapy in CP in Iran, that two of them have NCT number. Because of the increasing popularity of postnatal umbilical cord stem cell storage, the most easily accessible current source of stem cells in clinical trials is umbilical cord derived stem cells.

The least invasive source of stem cells, with the fewest ethical issues and with low

processing requirements, is umbilical cord blood (UCB). Safety of allogeneic UCB stem cells confirmed in several clinical trials. UCB is the most easily accessible current source of stem cells in our country. Well-matched allogeneic UCB has been used successfully in children for a number of decades so the risks of using this stem cell source are somewhat understood. There is evidence of in vitro differentiation of UCB into neuronal cells. Umbilical cord-derived mesenchymal stem cells is another source of effective and safe stem cells.

For the first time in our country we planned a trial of stem cells with mesenchymal stromal cells (MSC) derived from umbilical cord (UC), for the treatment of cerebral palsy.

Objectives:

This study designed for the evaluation of safety and therapeutic effects of intrathecal hematopoietic (MNC) and mesenchymal stem cells (MHC) derived from allogeneic umbilical cord in change and probable improvement of developmental functions of spastic CP participants in comparison with control group .

Study design:

Cases of Diparetic and Quadiparetic spastic CP between 4-14 years old selected among the patients referred to the pediatric neurology outpatient department of Children's Medical Center Hospital (CMC) affiliated to Tehran University of Medical Sciences. Due to necessity of HLA matching of hematopoietic stem cells derived from allogeneic umbilical cord (MNC) group we selected 150 cases of referred patients with our inclusion criteria and HLA analysis were done for these patients and then 36 cases of class 6 matched patients enrolled to the MNC group and 72 cases among the remaining patients randomly divided to mesenchymal stem cells derived from allogeneic umbilical cord (MSC) and control group . Therefore 108 cases enrolled in 3 divided groups of 36 patients.

Baseline clinical and neuroimaging evaluations were done for all of the 108 cases. Patients admitted in CMC and five million cell /kg of MNC and one million cell / kg of MHC stem cells that prepared in Royan Stem Cell Technology Co and Cell Tech Pharmed Co respectively were injected intrathecally with sedation. Only one dose of intrathecal injection was done for each participant .In the control group after insertion of the needle into the skin with an appearance of simulation of lumbar puncture no injection were done without the awareness of the patients or their parents. All of the participants admitted for observation and management of early side effects and discharged after 24 hours. Acute side effects and probable long term side effects will be reported and noted on our preformed questioners . Both participants and clinical evaluators are not aware of the 3 divided groups and our study is double blind.

Follow up clinical evaluators will be done at 1, 3, 6, and 12 months after injection for all of the participants .The intervention and control groups referred for neurorehabilitation with an identical protocol , that will be continued during the 12 months of follow up .

Standard brain Magnetic Resonance Imaging (MRI) with Magnetic Resonance Spectroscopy (MRS) and Diffusion Tensor Imaging (DTI) were done before injection and will be repeated after 12 months of clinical follow up.

For ethical consideration, we promised in the consent form that stem cell therapy will be done free of charge for participants of control group after 12 months of evaluation.

Inclusion criteria:

- Spastic cerebral palsy (Diparetic , Quadriparetic)
- Ages between 4 - 14 years
- Gross motor function classification (GMFC) between 2 -5
- No seizure disorder or with controlled seizures

- Evidence of definite acquired abnormal imaging findings compatible with Cerebral Palsy
- Informed consent is taken from their parents

Exclusion criteria:

- Normal brain MRI
- Progressive neurologic diseases
- Cortical malformations
- TORCH (Toxoplasmosis, Other, Rubella, Cytomegalovirus and Herpes Infections)
- Other types of cerebral palsy including athetoid , atonic , ataxic , and mixed type
- Acute intercurrent infections such as Hepatitis C Virus (HCV), Hepatitis B Virus (HBV), Human Immunodeficiency Virus (HIV) Malignancies
- Hemorrhagic diathesis
- Severe anemia (Hemoglobin less than 8 g/dl)
- Ventilator dependent pulmonary diseases
- Renal insufficiency
- Severe liver dysfunction

Primary outcome measures:

Different scoring systems such as Gross Motor Functional Classification System (GMFCS) , Gross Motor Function Measure Score (GMFM66) , Manual Ability Classification System (MACS) , Pediatric Evaluation of Disability Inventory (PEDI) , CP Quality of Life (QOL) , Life Habits Questionnaire and Modified Ashworth scale for spasticity were done at baseline and then will be repeated in follow ups until 12 months of final evaluation.

Change and Improvement to baseline of motor function with GMFCS score
Change and Improvement to baseline of motor function with Gross Motor Function Measure Score (GMFM66)
Change and Improvement to baseline of Manual Ability Classification System (MACS)
Change and Improvement to baseline of Pediatric Evaluation of Disability Inventory (PEDI).
Improvement of CP QOL
Improvement of Life Habits Questionnaire
Change and Improvement to baseline of Spasticity of patients according to Ashworth scale.
Improvement of developmental status according to Stanford Binet scale.

Secondary Outcome Measures:

Change and Improvement to baseline of Brain imaging findings according to MRI, MRS and DTI (baseline and at 12 months after injection)

Ethic Committee Approval:

Tehran University of Medical Sciences - 2017-06-06

Ethics committee Reference number: IR.TUMS.VCRREC.1996.2506.

Iranian Registry of Clinical Trials (IRCT) :

Trial Id No 7342 Registration date 2017-07-12 - IRCT201706176907N13

Sample size calculation:

To determine the sample size and attainment the maximum power, Sample size was calculated, based on the standard deviation reported from the study of Zali A,

et.al(($\sigma=10$) and Type I (α) error 0.05 and power 80% to achieve 12 score difference in mean of GMFC after intervention. The minimum number of patients required for this study was estimated 108 subjects, which are in each of the three groups MNC, MSC and Control 36 patient allocated, respectively.

Number of subjects N in each of two groups (Diggle *et al.*, 2002)

$$N = \frac{2(z_{\alpha} + z_{\beta})^2 (1 + (n - 1)\rho)}{n[(\mu_1 - \mu_2)/\sigma]^2}$$

- σ^2 is the assumed common variance in the two groups
- $\mu_1 - \mu_2$ is the difference in means of the two groups
- n is the number of timepoints
- ρ is the assumed correlation of the repeated measures

Randomization:

The patients are randomly allocated into three groups of intervention and control using a balanced block randomization technique. To do that, they were divided into blocks of 6 and 9. All subjects randomly allocated with online randomization software to generate random-number sequences. {Sealed Envelope Ltd. 2015.

Create a blocked randomization list. [Online] Available from:

<https://www.sealedenvelope.com/simple-randomiser/v1/lists> [Accessed 15 Dec 2015]}. Coordinator and Physician responsible for assessing inclusion / exclusion criteria and registering individuals are blind.

Due to necessity of HLA matching of hematopoietic stem cells derived from allogeneic umbilical cord (MNC) group we selected 150 cases of referred patients with our inclusion criteria and HLA analysis were done for these patients and then

36 cases of class 6 matched patients enrolled to the MNC group and 72 cases among the remaining patients randomly divided to mesenchymal stem cells derived from allogeneic umbilical cord (MSC) and control group . Therefore 108 cases enrolled in 3 divided groups of 36 patients.

Statistical analysis:

Intent-to-treat approach will be used to compare the mean GMFC as the initial outcome among the three groups. One-way analysis of variance will be used to investigate the difference between mean GMFC according to the study variables. Then, the post-hoc Scheffe test is used to determine the means differences. Moreover, backward stepwise multivariate linear regression will be used to evaluate the relationship between variables. The GEE model is used to evaluate the outcome changes over time. All analyses were performed at a significance level of 0.05 using the Stata 11 (StataCorp, College Station, TX, USA) statistical software.

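### The plan calls all three groups randomised, but the MNC arm is filled by HLA match, so neither MNC comparison is protected by randomisation

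*Combined protocol and SAP*

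**What the plan says.** The document gives two accounts of how patients reach the three groups: umbilical cord hematopoietic cells (MNC), mesenchymal cells (MSC, in places written MHC) and control.

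- **Three-arm randomisation.** The study design paragraph of the Brief Summary has the 108 patients "randomly divided in 3 groups of MNC, MHC and control participants". The Randomization section opens with "The patients are randomly allocated into three groups of intervention and control using a balanced block randomization technique", adds that "they were divided into blocks of 6 and 9", and continues: "All subjects randomly allocated with online randomization software to generate random-number sequences".
- **HLA match, then two-arm randomisation.** The Study design section of the Detailed description, and the second paragraph of Randomization, say that 150 eligible patients were HLA typed because the MNC product requires matching. They then state: "36 cases of class 6 matched patients enrolled to the MNC group and 72 cases among the remaining patients randomly divided". Those 72 are split between MSC and control.

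The Statistical analysis section does not distinguish the contrasts: "Intent-to-treat approach will be used to compare the mean GMFC as the initial outcome among the three groups". The test is a one-way ANOVA, after which "the post-hoc Scheffe test is used to determine the means differences". In addition, "backward stepwise multivariate linear regression will be used to evaluate the relationship between variables", and a GEE model is planned for changes over time. No covariates are named for either model, and neither is linked to the way patients were allocated.

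**The concern.** Randomisation is what allows a difference between groups to be attributed to treatment. If MNC patients enter because they match a cord unit, and the other two arms are drawn from those left over, a difference between MNC and either other arm may reflect who entered the arm. The stated objective is to compare both cell products with control, so one of the two main efficacy questions is affected. Reporting the study as a three-arm randomised trial would overstate the evidence for MNC.

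**Working it through.** **1. The patient counts (Study design; Randomization).**

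- The plan's total reproduces: 36 MNC + 72 others = 108, or 36 per group.
- Left after MNC is filled: 150 − 36 = 114.
- Typed but not used: 114 − 72 = 42. The text does not say how the 72 were picked from the 114, or whether the 36 were all the matched patients or a subset.
- Randomised under this account: 72 of 108 (67%), and one of three pairwise contrasts.

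**2. Can the two accounts be combined?** HLA screening followed by three-arm randomisation of matched patients would be coherent, but it is not what is written. Matched patients go to MNC, and MSC and control come from those remaining. No patient is described as having a random chance of either MNC or another arm.

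**3. Block sizes.** A block of 6 splits evenly over three arms (2 each) or two (3 each). A block of 9 splits over three arms (9/3 = 3) but not over two (9/2 = 4.5). The stated blocks fit a three-arm list and not the two-arm randomisation of the 72.

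**4. What an imbalance would do to the planned tests (illustration only).** SD 10 comes from Sample size calculation and 36 per group from the plan. Assumed: the analysed outcome in MNC is shifted by d points against both other arms, MSC equals control, and there is no true treatment effect. An SD of 10 also presumes a score such as GMFM-66, because the GMFC classification in the inclusion criteria runs only from 2 to 5.

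- Standard error of a pairwise difference: 10 × √(2/36) = 2.357.
- Scheffe threshold: F(0.95; 2, 105) = 3.083, so critical |t| = √(2 × 3.083) = 2.483. The minimum significant difference is 2.483 × 2.357 = 5.85 points.
- MNC-control rejection: noncentral t, 105 df, noncentrality d/2.357.
- Omnibus F: noncentrality 36 × (2/3) × d²/100 = 0.24d², which is 0.96, 2.16 and 6.0 for d = 2, 3 and 5.
- At least one MNC contrast rejected: simulation, 400,000 runs.

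| Shift d | MNC-control (Scheffe) | At least one MNC contrast | Omnibus F | MSC-control |
|---|---|---|---|---|
| 0 | 1.5% | 2.7% | 5% | 1.5% |
| 2 | 5.5% | 9.5% | 12.7% | 1.5% |
| 3 | 11.8% | 19.5% | 23.5% | 1.5% |
| 5 | 36.3% | 51.7% | 57.1% | 1.5% |

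The documents give no figure for the imbalance. The table shows what a given shift would do, not how likely it is.

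**5. What the randomised comparison can carry alone.** For MSC versus control with 36 per arm and the plan's difference of 12 and SD 10, the standardised difference is 12/2.357 = 5.09. Power is 99.9% by two-sample t test (70 df, two-sided 0.05) and 99.5% at the Scheffe threshold. The difference detectable with 80% power by t test is 6.70 points. These figures allow for no dropout.

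**The case against.** The best defence is that the HLA route is disclosed, with its reason, inside the Randomization section itself. The opening sentences can then be read as a loose overview and the HLA paragraph as the real procedure. That makes the fault a wrong label and not a concealed departure. The point is fair, but the label is repeated in the summary, the block sizes follow it, and the analysis relies on it.

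Second, nothing in the documents links HLA match to motor outcome, and the shifts above were chosen for illustration; 5 points is half the plan's SD. This stands: the rejection rates should carry no weight in judging how serious the problem is. But the plan gives no argument that matching is unrelated to prognosis, and the unexplained choice of the 72 is a separate route to imbalance in the MNC contrasts. That choice does not harm the internal validity of MSC versus control.

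Third, Primary outcome measures lists change from baseline for the motor scales, and the GEE concerns change over time. Analysing change would remove part of a baseline-level difference. It would not remove a difference in expected course, and the ANOVA is stated for mean GMFC, not for change.

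Fourth, the stepwise regression is meant to explore relationships and need not be dropped for that use. True, but because it names no covariates and may discard a confounder, it cannot serve as the adjustment.

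**Conclusion.** The concern holds and must be fixed. The plan contradicts itself on allocation. Under the more specific account, which appears twice and gives its reason, 36 of 108 patients and two of three pairwise contrasts are non-randomised. MSC versus control is still described as randomised, although the stated block of 9 does not fit it. The analysis treats the three contrasts as equivalent and contains no prespecified safeguard.

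This conclusion rests on the text alone. Whether the MNC contrasts are in fact biased, by how much and in which direction cannot be determined from the documents; they are open to confounding, not shown to be confounded.

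**What to change.** 1. Replace the conflicting text in the Brief Summary, Study design and Randomization sections with one allocation statement. It should say how MNC patients were identified, whether all matched patients were taken, how the 72 were chosen from the 114, and which block sizes were used.
2. If MNC was filled by HLA match, delete the three-group randomisation claim. Present MSC versus control (72 patients) as the randomised intention-to-treat comparison, and label MNC-control and MNC-MSC as non-randomised wherever they are reported.
3. Estimate the two MNC contrasts with a prespecified model adjusted for baseline variables already collected, such as GMFM-66, GMFCS level, age and diparetic or quadriparetic type, and not by backward selection. If every matched patient is in MNC, match status coincides with arm and cannot itself be adjusted for; the report should say so.
4. If the three-group ANOVA is kept, give it the same label.

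The cost is protocol and SAP wording plus one adjusted model, with no extra patients and, on the plan's own inputs, ample power for MSC versus control. The price is that the MNC result is presented as weaker evidence, and adjustment cannot remove unmeasured differences.

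### The outcome used to size the trial, mean GMFC, is spelled out only as a classification with entry levels 2 to 5, where a difference of 12 with SD 10 cannot occur

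*Combined protocol and SAP*

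**What the plan says.** The sample size calculation takes its standard deviation from an earlier study ("Sample size was calculated, based on the standard deviation reported from the study of" that study, σ = 10). It sets alpha at 0.05 and power at 80%, and aims "to achieve 12 score difference in mean of GMFC after intervention". It concludes: "The minimum number of patients required for this study was estimated 108 subjects", that is 36 in each of three groups. The formula shown is for repeated measures, but no values are given for the number of timepoints n or the correlation ρ, and sidedness is not stated.

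The statistical analysis section uses the same label. It will "compare the mean GMFC as the initial outcome among the three groups" by one-way analysis of variance, after which "the post-hoc Scheffe test is used to determine the means differences".

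GMFC is expanded once, in the inclusion criteria: "Gross motor function classification (GMFC) between 2 -5". The primary outcome list does not use that abbreviation. It has eight unranked entries, among them "Change and Improvement to baseline of motor function with GMFCS score" and, as a separate entry, the GMFM66 motor score. Nothing in the document equates GMFC with GMFM66.

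**The concern.** A classification entered at levels 2 to 5 cannot show a difference of 12 between group means, or an SD of 10. Either the label is wrong, or the numbers come from another scale.

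This matters because the sample size and analysis sections are the only places that single out one of the eight primary outcomes. If their label fits one listed instrument and their numbers fit another, the plan does not say which score the main test uses. Nor is the analysis of variance tied to one of the visits at 1, 3, 6 and 12 months. The instrument and the visit could then be chosen after results are known, and a reader could not tell. The stated 80% power also cannot be relied on for the outcome as named.

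**Working it through.** **Inputs from the documents:** difference 12, SD 10, alpha 0.05, power 80%, 36 per group, entry levels 2 to 5, follow-up at 1, 3, 6 and 12 months.

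**Assumed:** two-sided test; 5 as the highest level (step 1 only); ρ over a range; 20% loss as an illustration (36 × 0.8 = 28.8, taken as 29 per group).

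**Step 1. Bounds if 5 is the top level.** The largest SD on a scale of width R is R/2.

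| Scale | Width (largest difference) | Largest SD |
|---|---|---|
| Levels 2 to 5 | 3 | 1.5 |
| Levels 1 to 5 | 4 | 2.0 |
| Change from entry at 2–5 to follow-up at 1–5 (−4 to +3) | 7 | 3.5 |

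Even against the loosest row, the plan's figures are too large: 12/7 = 1.7 times the largest difference and 10/3.5 = 2.9 times the largest SD.

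**Step 2. Without assuming a top level.** For two means 12 apart on a scale of width R, the largest common variance arises when the means sit symmetrically, and equals (R − 12)/2 × (R + 12)/2 = (R² − 144)/4. Setting this to 10² = 100 gives R = √544 = 23.3. In whole levels the width is 24, so levels 1 to 25. For change scores with entry at 2 to 5 and top level K at follow-up, the width is K + 2, so K must be at least 22.

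**Step 3. Does 36 follow from 12 and 10 on some other scale?** The plan's formula is N = 2(zα + zβ)²(1 + (n − 1)ρ) / (n[(μ1 − μ2)/σ]²).

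- One timepoint: 2 × (1.960 + 0.842)² / 1.2² = 2 × 7.849 / 1.44 = 10.9, so 11 per group.
- Four timepoints: 2.7, 5.2, 6.8, 10.1 and 10.9 for ρ = 0, 0.3, 0.5, 0.9 and 1.
- One-sided: at most 8.6.

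Because (1 + (n − 1)ρ)/n never exceeds 1 for ρ up to 1, no choice of n and ρ gives more than 10.9. Other routes also fall short of 36: Bonferroni for two or three comparisons gives 14 to 15, the three-group analysis of variance 12 to 15, a Scheffé pairwise contrast 16, and 10 to 30% loss applied to 11 gives 13 to 16. The plan's figure is not reproduced. At one timepoint, 36 would need a difference of about 6.6 with SD 10, or an SD of about 18.2 with a difference of 12.

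**Step 4. Power for 12 with SD 10, one timepoint.**

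- Unadjusted, 36 per group: z = 1.2 × √18 − 1.960 = 3.13, power 99.9%. With 29 per group: 99.5%.
- Scheffé, 36 per group: critical t = √(2 × F0.95(2, 105)) = 2.483; noncentral t power 99.5%. With 29 per group: critical value 2.492 on 84 df, power 98.0%.

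**Step 5. Difference detectable at 80% power, only if SD 10 applies to the chosen instrument.**

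| One timepoint | Unadjusted | Scheffé |
|---|---|---|
| 36 per group | 10 × 2.802 × √(2/36) = 6.6 | 7.9 |
| 29 per group | 10 × 2.802 × √(2/29) = 7.4 | 8.8 |

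With four timepoints in the plan's formula and 36 per group, the unadjusted values are 4.6, 5.2 and 6.4 for ρ = 0.3, 0.5 and 0.9. The unadjusted figures use the normal approximation.

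**The case against.** The best defence is that GMFC is a clerical slip. Its expansion stands in an eligibility criterion, not in an outcome definition, and the document is loose with abbreviations elsewhere: the Study design section calls the mesenchymal cells both MHC and MSC. If GMFM66 was meant and SD 10 is right, the trial has at least 98% power for 12 points even after 20% loss, so the error is conservative. If the classification was meant, power is unknown, which is not the same as inadequate. The plan also does fix the groups, an intent-to-treat approach, the test and the post-hoc method.

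Much of this stands. The slip is plausible, and what is missing from the main comparison is the instrument and the timepoint, not every element. But correcting the label alone does not rescue the calculation, because step 3 shows that 12 and 10 do not lead to 36 on any scale. Neither reading makes the text right, and the document does not say which was intended.

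It is also fair that the detectable differences depend on an SD whose scale is unverified, and that the four-timepoint values concern a time-averaged difference, not a single-visit analysis of variance. They are illustrations only.

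**Conclusion.** The power statement is wrong as written under either reading, and the main outcome is not identified. This needs correcting before analysis.

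- **If the classification is meant:** 12 with SD 10 is impossible on any scale narrower than 23.3 points. No difference or SD in levels is given, so power cannot be stated.
- **If GMFM66 is meant and SD 10 is right:** the trial is larger than its stated inputs require (36 against at most 11 per group), and the error is on the safe side.

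The impossibility does not rest on 5 being the top level; only the bounds in step 1 do. The sample size and power figures assume a two-sided 0.05 test. Which reading is right cannot be settled from the documents, since the cited study is not among them.

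**What to change.** 1. Check the cited study for the instrument behind SD 10. Record separately where the 12 comes from, since the text attributes only the SD to that study.
2. Name one instrument and one timepoint (for example the final evaluation at 12 months) as the main outcome, in the same words in the primary outcome, sample size and statistical analysis sections. Do this by dated amendment before unblinded outcome data are seen; if they have been seen, say so.
3. State the difference, SD, sidedness and expected loss on that scale. Give n and ρ as well if a repeated-measures comparison is kept; with one timepoint ρ drops out of the formula.
4. Keep 36 per group, since the Study design section reports the 108 as already enrolled. Replace the claim of 80% power for 12 points with the power or detectable difference that follows from item 3. The step 5 values can be used only if SD 10 is confirmed for the chosen instrument.
5. If the classification is kept as the main outcome, re-derive the power in levels, with an analysis suited to ordinal data.

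The cost is one source check and one amendment touching three sections. No patients or assessments are added: GMFCS and GMFM66 are both already planned at baseline and through 12 months. The document describes baseline and injection in the past tense and follow-up in the future tense, so timing is the main constraint.

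### The stated inputs and printed formula give at most 11 patients per group, not 36, so the minimum of 108 and the 80% power for 12 points do not follow from them

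*Combined protocol and SAP*

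**What the plan says.** The section on sample size calculation takes a standard deviation of 10 from a cited study and sets "Type I (α) error 0.05 and power 80% to achieve 12 score difference in mean of GMFC after intervention". It concludes: "The minimum number of patients required for this study was estimated 108 subjects", allocated as 36 to each of MNC, MSC and control.

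The formula printed beneath is headed "Number of subjects N in each of two groups":

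N = 2(z_α + z_β)² (1 + (n − 1)ρ) / ( n [(μ1 − μ2)/σ]² )

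Here n is the number of timepoints and ρ "is the assumed correlation of the repeated measures". No value is given for either. The section does not say whether α is one- or two-sided, and it mentions no allowance for dropout or for multiple comparisons.

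The statistical analysis section compares the mean of the initial outcome across three groups by one-way ANOVA, followed by Scheffe. It adds a GEE model for change over time, and states: "All analyses were performed at a significance level of 0.05".

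**The concern.** A 12-point difference with an SD of 10 is a standardised effect of 1.2, which is very large. Comparing two means at that effect size takes about a dozen patients per group, so 36 is about three times too many to be the minimum for 80% power.

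The discrepancy matters for three reasons:

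- **Reading a null result.** Readers will take the trial as having 80% power for 12 points. On the stated SD it can detect much smaller differences. If the SD really assumed was nearer 18, it cannot.
- **Justifying exposure.** Children aged 4 to 14 receive a sedated intrathecal injection or a simulated lumbar puncture. An ethics committee needs to be able to trace the number exposed to the assumptions.
- **Matching the analysis.** The formula sizes a repeated-measures comparison of two groups. The comparison named for the initial outcome is a three-group ANOVA with Scheffe.

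**Working it through.** **Inputs**

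| Input | Value | Source |
|---|---|---|
| SD | 10 | Sample size calculation |
| Difference | 12, i.e. 1.2 SD | Sample size calculation |
| Alpha | 0.05, sidedness not stated | Sample size calculation |
| Power | 80% | Sample size calculation |
| n (timepoints) | Not stated; 4 follow-up visits, 5 with baseline | Study design: "Follow up clinical evaluators will be done at 1, 3, 6, and 12 months after injection for all of the participants" |
| ρ | Not stated | Assumption; range 0 to 1 examined |

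**1. Trying to reproduce 36 per group.** With two-sided alpha, z_α + z_β = 1.960 + 0.842 = 2.802, whose square is 7.849. The formula becomes

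N = (2 × 7.849 / 1.44) × (1 + (n − 1)ρ)/n = 10.90 × (1 + (n − 1)ρ)/n.

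The last factor equals 1 when n = 1 or ρ = 1, and is below 1 whenever n > 1 and ρ < 1. So 10.90, or 11 per group and 33 in total, is an upper bound that does not depend on the unstated values.

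| n | ρ | N per group before rounding up |
|---|---|---|
| 1 | any | 10.90 |
| 4 | 0 | 2.73 |
| 4 | 0.5 | 6.81 |
| 4 | 0.7 | 8.45 |
| 4 | 0.9 | 10.08 |
| 5 | 0.5 | 6.54 |
| 5 | 0.9 | 10.03 |

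With one-sided alpha the ceiling is 8.59, or 9 per group.

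**2. Conventions the plan does not mention.** Each row uses SD 10, a difference of 12 and a single timepoint.

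| Variant | Per group |
|---|---|
| Two-sample t-test instead of normal approximation | 12 |
| Three-group ANOVA F test, means (0, 0, 12) or (0, 6, 12) | 12 or 15 |
| Bonferroni over three pairs | 15 |
| 90% power | 15 |
| Scheffe pairwise | 16 |
| Bonferroni over 8 primary outcomes × 3 pairs | 22 |
| The same, with 90% power | 27 |

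None reaches 36. Dropout inflation alone would need 1 − 11/36 = 69% attrition.

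**3. What 36 per group delivers at SD 10.** The standard error of a pairwise difference is 10 × √(2/36) = 2.357, so 12 points is 12/2.357 = 5.09 standard errors.

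- Unadjusted power for 12 points is Φ(5.09 − 1.96) = 99.9%; the t-test gives the same.
- The Scheffe critical value is √(2 × F(0.95; 2, 105)) = 2.483, and the power is 99.5%.
- The difference detectable with 80% power at a single timepoint is 6.7 points by t-test and 7.9 points under Scheffe.
- By the printed formula that difference is 2.802 × 2.357 = 6.6 points at most. With n = 4 it is 5.2, 5.8 and 6.4 points for ρ = 0.5, 0.7 and 0.9.

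**4. What would make 36 the 80% size for 12 points.** Solving the formula for the SD gives 12 / (2.802 × √(2/36)) = 18.2 at n = 1 or ρ = 1. That is a lower bound: at n = 4 and ρ = 0.5 it is 23.0.

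**The case against.** The strongest reply is that the error is on the safe side. If SD 10 and 12 points are the real assumptions, 36 per group gives far more than 80% power and makes a null result more informative. The section also opens by naming maximum power as an aim, and the study design reports baseline assessment of all 108 patients as done, so a correction would not change exposure. All of this stands, and the trial should not be called underpowered on the stated inputs. It does not rescue the word minimum or the 80% figure, and the reassurance holds only if the written inputs are the true ones. The SD rests on a cited study, so the documents cannot show which input, if any, is misreported.

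A second reply is that an allowance was made but not written down, for 12 months of dropout or for several primary outcomes. That is possible and the sponsor should say so, but none of the common allowances tried gets close on its own.

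A third is that the planned GEE model makes a repeated-measures formula reasonable. That is fair for that analysis, but a repeated-measures gain lowers N further, and the comparison named for the initial outcome is still ANOVA with Scheffe.

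One benign explanation is that the t-test answer of 12 per group, 36 in total over three groups, was carried forward as a per-group number. The documents do not confirm it and the finding does not need it.

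**Conclusion.** The concern holds. From the plan's own inputs and formula the requirement is at most 11 per group (33 in total), against 36 per group (108) stated, a factor of about 3.3. The bound needs only two-sided alpha and ρ no greater than 1; one-sided alpha lowers it to 9. The accompanying claim, "power 80% to achieve 12 score difference in mean of GMFC after intervention", understates the power of 36 per group, which is 99.9% unadjusted and 99.5% under Scheffe. These power figures assume SD 10, a single-timepoint comparison and no missing data. Whichever score the outcome label refers to, the arithmetic is the same.

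**What to change.** Rewrite the sample size paragraph so that it can be reproduced:

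- State the n, ρ, sidedness, multiplicity rule and any dropout inflation actually used, and which analysis the calculation serves.
- If SD 10 and 12 points are right, drop the claim that 108 is the minimum and report what 36 per group gives: over 99% power at 12 points, and 80% power for about 6.7 points per pairwise comparison (about 7.9 under Scheffe). If the repeated-measures analysis is the basis, give the detectable difference for the stated n and ρ, which is at most 6.6 points.
- If a larger SD or a smaller difference was intended, write that and its source. For 12 points the SD would have to be at least 18.2.
- If the extra patients serve safety, secondary outcomes or attrition, say so.

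The cost is one rewritten paragraph, with no change in enrolment.
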